6.1.1. Bladder Diary Endpoints

Refer to parameter derivations from Bladder Diary data in Section 4.3.1. Scheduled post-treatment visits for bladder diary endpoints include Weeks 2, 4, 8, 12, 16, 24, 28, 36, and 52.

CFB to Week 52 in average daily number of micturition episodes

This analysis will be done on the FAS-Ext set and repeated on the PP-Ext set, with no additional covariates.

CFB to Week 52 in average daily number of urgency episodes

This analysis will be done on the FAS-Ext set and repeated on the PP-Ext set, with an additional categorical covariate of average number of micturition episodes per day (≤ 12 vs. > 12).

CFB to Week 52 in the average nightly number of nocturia episodes

This analysis will be done on the FAS-Ext set and repeated on the PP-Ext set, with no additional covariates.

CFB to Week 52 in the average daily number of UUI episodes for subjects with baseline incontinence in study URO-901-3005

This analysis will be done on the FAS-Ext-I set and repeated on the PP-Ext-I set, with no additional covariates.

CFB to Week 52 in the average volume voided per micturition

This analysis will be done on the FAS-Ext and PP-Ext sets, with no additional covariates.

[figure not shown]
6.1.2. IPSS Endpoint

Refer to endpoint definitions in section 4.3.2.1. Scheduled visits for the IPSS include Weeks 4, 8, 12, 24, 36, and 52.

CFB to Week 52 in the IPSS storage score (1-week recall)

This analysis will be done on the FAS-Ext set and repeated on the PP-Ext set, with no additional covariates.

6.2. Exploratory Endpoints

6.2.2. Other Quality of Life Endpoints

The FAS-Ext will be the analysis population for the PRO data unless stated otherwise.

6.2.2.1. CFB in [REDACTED] Scores

6.2.2.3. Patient Global Impression Scores

The questionnaire is assessed at baseline, Weeks 4, 12, 24, and 52 for the 52-week treatment group, and baseline and Week 28 (Week 52 relative to the start of URO-901-3005) for the 28-week treatment group. The Patient Global Impression (PGI) questions are designed to assess a

subject’s overall impression of OAB in 5 categories: [REDACTED]
 [REDACTED]

Each of the responses to the PGI questions will be assigned a numerical value starting from 1. A higher score represents a worse outcome in each category.

Table 8: PGI Scoring

PGI Category	Score
[REDACTED]	1 = None 2 = Mild 3 = Moderate 4 = Severe
[REDACTED]	1 = Complete control 2 = A lot of control 3 = Some control 4 = Only a little control 5 = No control
[REDACTED]	1 = Never 2 = Rarely 3 = Sometimes 4 = Often 5 = Very often
[REDACTED]	1 = Much better 2 = Moderately better 3 = A little better 4 = No change 5 = A little worse 6 = Moderately worse 7 = Much worse

The questions [REDACTED] PGI-Control, PGI-Frequency and PGI-Leakage are ordinal assessments going from lower impact of disease to highest impact of disease with score with scores ranging from 1 to 4 for [REDACTED] and 1 of 5 for [REDACTED]. These questions will be summarized descriptively as numerical variables of score and change from baseline by treatment group and visit. Additionally, these questions will be analyzed as categorical variables with count and percent for each category by treatment group and visit.

The [REDACTED] question is asked relative to baseline. The score will only be summarized as a categorical variable with count and percent for each category by treatment group and visit.

The FAS-Ext will be the analysis set for all categories except for [REDACTED]. The FAS-Ext-I will be the analysis set for the [REDACTED] analysis.

7. SAFETY ANALYSIS

The SAF-Ext will be used for all safety analyses. Safety will be assessed based on extent of exposure and compliance, AE reports, clinical laboratory data, physical examinations, vital signs, post-void residual volume, and total IPSS score.

No inferential statistical testing is planned on the safety data, all data will be summarized and listed only.

7.1. Extent of Exposure

The duration of exposure with vibegron over studies URO-901-3005 and URO-901-3006 will be expressed as the time in days from the first dose of vibegron as recorded on the Study Drug Administration CRF page through to last treatment day (inclusive) as recorded on the End of Treatment CRF page, excluding any days where it is recorded that an interruption has occurred on the AE CRF page. If no last treatment date is recorded, it will be imputed as the minimum of the date of the last visit on study 3006 and the date when last dispensed study treatment was scheduled to be exhausted (last dispensation date + number of doses dispensed).

Interruptions to dosing can be due to delays in resupply (measured by gaps in the study drug log) or interruptions due to AE. Interruptions due to AE that overlap partially or completely will be listed separately but not double-counted for summing interruption days.

Gaps in the study drug log will be determined by comparing the dispensation date of a record to the previous dispensation date (where up to four bottles may have been dispensed). The gap is measured from the study day of previous dispensation + number of pills dispensed + number of days of AE interruption within the period.

$$\text{Interruption in days} = \text{date interruption started} - \text{date interruption stopped} + 1$$

This is given by the following formula:

$$\text{Duration (days)} = \text{date of last vibegron dose} - \text{date of first vibegron dose} - \text{interruption days} + 1$$

Duration of exposure will be summarized by treatment group and overall for the SAF-Ext set using summary statistics for continuous variables. A listing will present the treatment start and end date together with date(s) of interruption and the overall duration of exposure.

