6.1. Study Drugs Administered

Table 1 Summary of Study Drugs

Study Drug Name	Vibegron
Dosage Formulation	tablet
Identity of Formulation	75 mg
Route of Administration	oral
Dosing Instructions	once daily
Packaging and Labeling	Study drug will be provided in HDPE bottles with child-resistant caps. Each bottle will contain 32 tablets and will be labeled as required per country requirement.
Manufacturer	Patheon, Cincinnati, Ohio, US
Number and Timing of Drugs	Treatment Period: 1 tablet daily

The study drug will be supplied in bottles each containing 32 tablets (4-week treatment and 4-day extra supply) and labeled with the protocol number, lot number, expiration date, study drug name (vibegron 75 mg tablets) and number of tablets, directions for use, storage information, warning language (*Keep Out of Reach of Children. For Clinical Trial Use Only. To be used by qualified investigators only. Caution: New Drug—Limited by United States Law to Investigational Use.*), and the US Sponsor name and address. Immediately before dispensing the study drug, the investigator (or appropriately trained designee) will write the subject number, visit no. and the dispense date on the detachable panel of the label, which also includes the protocol number, bottle number and lot number.

Subjects will take 1 tablet of study drug (vibegron) once daily for up to 28 weeks.

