10.7.3. Open-label Treatment Period, Visit 13 (Week 36 [Day 253 ± 4 days])

- Review AEs/SAEs
- Review concomitant medications
- Administer IPSS and [REDACTED] assessments
- Record blood pressure (3 results taken 1-2 minutes apart after sitting for 5 minutes), pulse, respiration, temperature, and weight
- Measure post-void residual volume
- Perform laboratory assessments
- Review and data enter completed Bladder Diary
- Dispense Bladder Diary
- Dispense open-label study drug

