4.2.4. Assessment Windows

4.2.4.1. Study Reporting Periods

Based on study design and variables under consideration, study time periods are defined as below.

Table 2: Definition of Study Reporting Periods

Analysis description	Analyzing Study Period	Start Date	End Date
General	Pre Treatment (Day -49 – Day 1/Week 24)	Date of informed consent	Prior to the date of first dose of vibegron on either study URO-901-3005 or URO-901-3006
	Treatment (Day 1/Week 24 – Week 52)	Date of first dose of vibegron on either study URO-901-3005 or URO-901-3006	Date of last dose of vibegron on URO-901-3006 + 5 or EOS, whichever is earlier
Adverse events	Prior (Summarized as Medical History)	Start date \geq date of informed consent on URO-901-3005 and $<$ date of first dose of vibegron in either study.	No restriction
	Treatment Emergent (TEAE)	Start date (AE begins or worsens in severity) \geq date of first dose of vibegron* and \leq date of last dose of vibegron + 5 days or EOS visit, whichever is earlier.	No restriction

Analysis description	Analyzing Study Period	Start Date	End Date
Prior or Concomitant Medication/ Procedure	Prior medication/ procedure	Start date < date of first vibegron dose	End date < date of first vibegron dose OR medication not marked as ‘ongoing’ on study URO-901-3005 and subject received placebo on study URO-901-3005
	Concomitant medication/ procedure	Start date \geq date of first dose of vibegron and \leq date of last vibegron dose + 5 days or EOS visit, whichever is earlier.	
		Start date < date of first vibegron dose, but ongoing during vibegron treatment period	End date \geq date of first vibegron dose OR medication marked as ‘ongoing’ on study URO-901-3005.

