7.3. Adverse Events

AEs will be coded using MedDRA version 23.0 or higher.

All reported AEs (whether treatment emergent or not) on both study URO-901-3005 and URO-901-3006 will be included in by-subject AE listings on the Safety Set Extension. Sorting will be by country, site, subject, date of event, SOC, PT and then verbatim description. An additional overall AE listing will be presented for subjects that were enrolled but not dosed with vibegron on URO-901-3006.

An AE will be considered treatment emergent (TEAE) if it begins or worsens in severity after the first dose of vibegron on study URO-901-3005 or URO-901-3006 through 5 days after the last dose of vibegron. Partial AE start dates will be imputed as detailed in [Section 4.2.3](#).

Summary tables will be based on TEAEs. The incidence of TEAEs will be presented using counts and percentages of subjects with TEAEs and tabulated by SOC and PT. SOC will be sorted in descending frequency and PT within SOC will be sorted by descending frequency based on the incidence across subjects overall. If a subject has multiple occurrences (start and stop) of an event associated with a specific SOC or PT within a SOC, a subject will only be counted once in the incidence count for the SOC or PT within SOC respectively.

An overall summary table of AEs will be presented detailing the number and percentage of subjects, and number of events for the following categories:

- At least one TEAE;

- At least one Treatment-Related TEAE;
- At least one Grade ≥ 3 TEAE (Mild = Grade 1, Moderate = Grade 2, Severe of Medically Significant = Grade 3, Life-Threatening = Grade 4, Death = Grade 5)
- At least one Grade ≥ 3 Treatment-Related TEAE;
- At least one Serious TEAE;
- At least one Serious Treatment-Related TEAE;
- At least one TEAE leading to Discontinuation from Study Medication;
- At least one TEAE of Special Interest;
- At least one Treatment-Related TEAE of Special Interest

Where not otherwise noted, all the following summaries are presented by PT:

- All TEAEs (by SOC and PT);
- Treatment-Related TEAEs (i.e., possibly or probably related);
- TEAEs occurring in 2% or more of the population;
- All TEAEs by SOC, PT, and maximum severity (where the maximum intensity per patient will be counted at each level of summarization);
- TEAEs with Grade ≥ 3 ;
- Treatment-Related TEAEs with Grade ≥ 3 ;
- Serious TEAEs;
- Treatment-Related Serious TEAEs;
- Fatal TEAEs;
- TEAEs leading to Discontinuation from Study Treatment;

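### With no last-dose date recorded, a man last seen at a dispensing visit is deemed to stop on the day he was resupplied, so on the natural reading his TEAE window closes 5 days later

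*SAP*

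**What the plan says.** SAP 7.1 (Extent of Exposure) defines duration from first to last dose of vibegron and covers a missing last date: "If no last treatment date is recorded, it will be imputed as the minimum of the date of the last visit on study 3006". The second term of that minimum is supply exhaustion, worded as "date when last dispensed study treatment was scheduled to be exhausted (last dispensation date + number of doses dispensed"). It notes that at one dispensation there can be several bottles: "where up to four bottles may have been dispensed".

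The treatment-emergent window depends on the same event. SAP Table 2 (4.2.4.1) requires AE onset no later than "date of last dose of vibegron + 5 days or EOS visit, whichever is earlier". SAP 7.3 counts onset or worsening "through 5 days after the last dose of vibegron", with no end-of-study cap. The concomitant-medication rows of Table 2 use the same 5-day limit. SAP 7.3 bases the AE summary tables on TEAEs, including the serious, special-interest and fatal ones. All AEs, treatment-emergent or not, go into by-subject listings, and deaths have a listing of their own.

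Protocol 6.1 supplies drug in "bottles each containing 32 tablets (4-week treatment and 4-day extra supply"). Protocol 1.3 and 10.7 dispense it at Visits 11, 12 and 13; the entry for Visit 13 (Week 36, Day 253) includes "Dispense open-label study drug". The next clinic visit is Visit 14 (Week 52, Day 365), with a telephone contact at Week 44 (Day 308).

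**The concern.** The earlier-of-two-dates rule is a reasonable way to avoid overstating exposure. As the end of an at-risk window for safety events it errs the other way. A man who has just been given tablets and then disappears is treated as never taking any of them beyond that day.

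The primary objective is long-term safety. Men lost while holding drug are the ones whose serious event or death is learned of late: through the Week 44 call, the three or more contact attempts in Protocol 7.3, or a later report under Protocol 8.4.1. Removing such an event lowers the tabulated incidence. Because incidence is a percentage of subjects, the shortened exposure does not offset the loss.

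The rule also runs against the SAP's own conventions. SAP 7.2 assumes, for bottles not returned, that dosing went on as directed until the next dispensation, the end of supply or a noted end of treatment. SAP 4.2.3 fills missing AE attributes cautiously: an unknown relationship becomes probably related and an unknown intensity becomes severe.

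**Working it through.** **Inputs.** Dispensing visits on Days 169, 197 and 253; Visit 14 on Day 365; Week 44 call on Day 308 (Protocol 1.3). Bottle size: 28 + 4 = 32 tablets, which reproduces Protocol 6.1. Up to four bottles per dispensation (SAP 7.1). Window: last dose + 5 days (SAP Table 2 and 7.3).

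**Assumption.** The documents do not say how many bottles go out at each visit. I take the fewest that reach the next clinic visit: 1 for 28 days, 2 (64 tablets) for 56 days, 4 (128 tablets) for 112 days. The imputed date does not depend on this, because any positive number of tablets puts exhaustion after the visit.

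**Formulas.** Imputed last dose = min(last visit, dispensation day + tablets dispensed). Window end = imputed last dose + 5. Days outside = next clinic visit − window end.

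| Last seen at | Exhaustion (SAP 7.1) | Imputed last dose | Window end | Days outside, of days to next clinic visit |
|---|---|---|---|---|
| Visit 11 | 169 + 32 = 201 | 169 | 174 | 197 − 174 = 23 of 28 (82%) |
| Visit 12 | 197 + 64 = 261 | 197 | 202 | 253 − 202 = 51 of 56 (91%) |
| Visit 13 | 253 + 128 = 381 | 253 | 258 | 365 − 258 = 107 of 112 (96%) |

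These are maxima: they assume Table 2's end-of-study limit does not close the window sooner.

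**If the Week 44 call took place and counts as a visit.** Imputed last dose = min(308, 381) = Day 308; window end = Day 313; 365 − 313 = 52 of the remaining 57 days (91%) are outside. A man lost or dead before that call is unaffected by this reading.

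**With the 21 days of Protocol 9.4.2 instead of 5.** 253 + 21 = Day 274, leaving 365 − 274 = 91 days outside. The longer window does not repair the problem.

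**Check against SAP 7.2.** For four bottles dispensed at Visit 13 and not returned, the compliance rule credits 128 doses if no end-of-treatment date is used. If the imputed date is used it credits min(128, 253 − 253 + 1) = 1 dose. The SAP does not say which applies.

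**Edge case.** A man from the placebo arm, last seen on Day 169, whose first tablet is recorded on Day 170, gets a duration of 169 − 170 + 1 = 0 days. This will be rare, but it shows that the rule needs a floor.

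**The case against.** - **The link is inferred.** The rule sits under extent of exposure, and neither Table 2 nor SAP 7.3 refers to it. This stands: the SAP does not state that the imputed date feeds the TEAE window. But the window cannot be computed without a last dose and no other rule is offered. If 7.1 is not meant to apply, the window is undefined for these men.
- **The supply date can come first.** A reader might infer that the supply term never operates. That is not so. With two bottles at Visit 12 (exhausted Day 261), Visit 13 missed and an early-withdrawal visit on, say, Day 280, the rule gives Day 261. The problem is confined to men whose last visit was a dispensing visit.
- **The Week 44 call may be a visit.** SAP 7.5 groups it with telephone visits, while Protocol 1.2 says no clinic visit is required then; SAP 7.1 does not define the term. If it counts, events up to Day 313 are kept for men who were reached.
- **Table 2 also stops at end of study.** Its note includes discontinuation and loss to follow-up. If a lost man's end of study is dated back to his last contact, the window closes there whatever 7.1 imputes. This stands, and the fix has to deal with it.
- **Few men, and nothing is concealed.** Treatment start and end dates are required source data (Protocol 10.1.8), and men who stop are asked for early-withdrawal assessments. Late events remain in the all-AE listing, with a TEAE flag, and in the listing of deaths. A data safety monitoring board reviews safety, and the study tests no hypotheses. All true, but the summary tables are where incidence is read.

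**Conclusion.** The point holds for a man with no recorded last treatment date whose last visit was Visit 11, 12 or 13. His last dose is set to the day of resupply. On the natural reading, events with onset more than 5 days later leave the TEAE, serious, special-interest and fatal TEAE tables. The largest gap is 107 days after Visit 13, or 52 days after the Week 44 call if that call counts.

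A reader might infer that 96% of late events are missed, or that deaths vanish from the report. The documents support neither. The percentages are shares of calendar time for an affected man, not of events, and the listings keep every reported case.

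The number of affected men is not given. Purely as an assumption, 1% to 5% of 300 would be 3 to 15 men, and fewer would also have a late event. No event rate is available, so the effect on incidence cannot be estimated. It is probably small in number, but one fatal event among 300 men is 0.33%, and it could be the difference between an empty fatal table and a non-empty one. The change is worth making because it is cheap and concerns the primary objective.

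**What to change.** 1. For the TEAE and concomitant-medication windows only, when the last-dose date is unknown set it to the earliest of supply exhaustion (last dispensation date + tablets dispensed − 1), date of death and end-of-study date. For four bottles at Visit 13 the supply term is 253 + 128 − 1 = Day 380.
2. State that for men lost to follow-up the end-of-study date is the date on which loss or death is documented, not the last visit. Otherwise the cap in Table 2 undoes the change.
3. Keep the SAP 7.1 minimum for the exposure-duration table, floored at the first dose date. Say whether the Week 44 call counts as a visit, and which end-of-treatment date SAP 7.2 uses.
4. Flag every event that is treatment-emergent only through this imputation.

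As a check, a fatal event with onset and death on Day 300, in a man supplied with four bottles at Visit 13 and not seen again, is outside the present window (Day 258). Under the new rule last dose is min(380, 300, end of study), which is Day 300 if end of study is not dated earlier, and the event counts.

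**Cost.** Some SAP wording and one derived variable. A few events in men who had already stopped will be counted as treatment-emergent, which is the cautious direction here, and the report must explain two last-dose dates. An event starting after loss has been documented would still fall outside Table 2's cap and be seen only in the listings.

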3.2. Violations and Deviation

Major protocol deviations are considered to have major impact on subject safety, efficacy or the validity of the study data.

Exclusion from per-protocol analysis is noted for each protocol deviation in the Protocol Deviation specifications. Patients with major protocol deviations that may impact efficacy results will be excluded from the PPS-Ext and PPS-Ext-I. Efficacy protocol deviations may include, but are not limited to the following:

- Subjects who do not meet the inclusion criteria
- Subjects who meet any of the exclusion criteria
- Concomitant use of prohibited medications
- Other (e.g., IP compliance < 70%)

Subjects excluded from the per protocol analysis in URO-901-3005 will also be excluded from per protocol analysis in URO-901-3006, with the exception of on-study protocol deviations in the placebo arm as noted in section 3.1.4.

The final list of major protocol deviations will be finalized and documented before database lock. All major protocol deviations related to efficacy will be discussed and finalized prior to database lock. Only major protocol deviations will be summarized and listed in the Clinical Study Report (CSR).

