4.3.3. Study Day and Duration

Study day is relative to the start date of the double-blind treatment on the parent study URO-901-3005. This is used to describe the relative time of an event or assessment that happened during the study. The first day of the study is defined as the day a patient first receives either vibegron or placebo in the double-blind treatment period. This is expected to be the same day as the randomization as Day 1. There is no study Day 0 defined in the study.

- For event or assessment that occurred on or after the first dose of double-blind treatment date:

$$\text{Study day} = \text{Date of event or examination} - \text{date of first study treatment} + 1$$
- For event or assessment that occurred prior to the first dose of double-blind treatment date:

$$\text{Study day} = \text{Date of event or examination} - \text{date of first study treatment}$$

Treatment day will be defined in the same manner relative to the date of first dose of vibegron.

Similarly, a duration between any two dates (such as AE duration) expressed in days will be calculated using the following conventions:

- $\text{Duration} = \text{Later date} - \text{earlier date} + 1$

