7.2. Treatment Compliance

Study treatment compliance (%) will be calculated as the actual number of vibegron doses taken divided by the expected number of vibegron doses, multiplied by 100 and summarized by treatment duration.

These numbers will be calculated as the sum of the number of tablets indicated as taken by the subject on each dispensation record. Where no treatment bottle is returned, and thus the actual number of doses taken is unknown, it will be assumed that the subject took medication as directed until another bottle was dispensed, their supply was exhausted, or end of treatment was noted. This is calculated as (minimum of [next dispensation date – dispensation date + 1], [doses dispensed] and [EOT date – dispensation date + 1]). Imputed values will be clearly noted in the listing.

The expected number of vibegron doses is the same as the calculated duration of exposure detailed in section 7.1.

Treatment Compliance will be summarized for the SAF-Ext and FAS-Ext population. Additionally, the number and percentage of subjects within each planned treatment duration with compliance in the following categories will be provided: <80%, 80 – 120%, and >120%. All data will be listed.

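### SAP 7.1 prints the interruption-days formula with its dates reversed, so interruptions of three or more days lengthen calculated exposure and expected doses instead of shortening them

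*SAP*

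**What the plan says.** SAP 7.1 (Extent of Exposure) states its aim in words: exposure runs from first to last vibegron dose across both studies, "excluding any days where it is recorded that an interruption has occurred on the AE CRF page". It recognises two kinds of interruption, those due to adverse events and those due to gaps in resupply.

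Two formulas follow. The first sets interruption days equal to "date interruption started" minus "date interruption stopped" plus 1. The second takes last dose date minus first dose date, subtracts the interruption days, and adds 1.

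SAP 4.3.3 (Study Day and Duration) has a general rule: "a duration between any two dates (such as AE duration) expressed in days will be calculated using the following conventions", namely later date minus earlier date plus 1.

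SAP 7.2 (Treatment Compliance) carries the result forward: "The expected number of vibegron doses is the same as the calculated duration of exposure detailed in section 7.1". Compliance is doses taken divided by that number, and is tabulated as below 80%, 80 to 120%, and above 120%. SAP 3.2 gives compliance below 70% as one example of a deviation that may remove a subject from the per-protocol sets.

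**The concern.** An interruption starts on or before the day it stops, so start minus stop is zero or negative. Apart from very short interruptions, the printed formula returns a negative number of days, and subtracting a negative number lengthens exposure. The formula therefore does the opposite of what the text above it says.

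Exposure is one of the items on which SAP 7 bases the safety assessment, and it is summarised by group and overall. As the compliance denominator, an inflated value also makes men with long interruptions look less compliant than they were. Interruptions are foreseen: Protocol 8.4.6.1 provides for temporary withholding with possible rechallenge, SAP 7.1 counts resupply gaps, and SAP 8 plans to list doses missed because drug was unavailable during the pandemic.

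**Working it through.** The plan gives no numerical result here, so there is no figure to reproduce. The check evaluates the printed formulas.

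**Inputs.** The interruption and exposure formulas are from SAP 7.1, the general duration rule from SAP 4.3.3, and expected doses from SAP 7.2. Planned courses are from SAP 1.2.1: 28 weeks × 7 = 196 days and 52 weeks × 7 = 364 days.

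**Assumptions.** There is one interruption of n days, the stop date is the last day off drug, and every other dose is taken. The documents give no interruption lengths.

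**Step 1, interruption days.** If the interruption starts on day s, it stops on day s + n − 1.

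- Printed: s − (s + n − 1) + 1 = 2 − n
- SAP 4.3.3: (s + n − 1) − s + 1 = n
- Difference: n − (2 − n) = 2n − 2

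**Step 2, exposure.** For a course of L days, the printed result is L − (2 − n) = L + n − 2 and the intended result is L − n.

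| n | Printed interruption days | L = 196: printed / intended | L = 364: printed / intended |
|---|---|---|---|
| 1 | 1 | 195 / 195 | 363 / 363 |
| 2 | 0 | 196 / 194 | 364 / 362 |
| 3 | −1 | 197 / 193 | 365 / 361 |
| 14 | −12 | 208 / 182 | 376 / 350 |
| 28 | −26 | 222 / 168 | 390 / 336 |

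**Step 3, compliance.** Doses taken are L − n, so calculated compliance is (L − n)/(L + n − 2). With the intended denominator it is 100%.

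- n = 14: 182/208 = 87.5% (L = 196); 350/376 = 93.1% (L = 364)
- n = 28: 168/222 = 75.7% (L = 196); 336/390 = 86.2% (L = 364)

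**Step 4, thresholds.** Solving (L − n)/(L + n − 2) < c gives n > [(1 − c)L + 2c]/(1 + c).

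- c = 0.80, L = 196: n > 40.8/1.8 = 22.7, so from n = 23 (173/217 = 79.7%)
- c = 0.80, L = 364: n > 74.4/1.8 = 41.3, so from n = 42 (322/404 = 79.7%)
- c = 0.70, L = 196: n > 60.2/1.7 = 35.4, so from n = 36 (160/230 = 69.6%)
- c = 0.70, L = 364: n > 110.6/1.7 = 65.1, so from n = 66 (298/428 = 69.6%)

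**Step 5, the other reading of the stop date.** If it is the day dosing resumes, day s + n, the printed formula gives 1 − n. One day off drug is then ignored, two or more days add n − 1, and the overstatement is 2n − 1. The direction is the same and the size differs by one day.

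**The case against.** The best reply is that this is a transposition with obvious intent. The prose in SAP 7.1 and the general rule in SAP 4.3.3 both point to the right order. SAP 2.2 plans dry runs before lock, SAP 4.2.2 requires program validation, and the exposure listing shows treatment dates, interruption dates and duration together, so an impossible value could be noticed. A slip in drafting is indeed the likely explanation. But dry runs and validation check programs against the plan, and here the plan is wrong. A value such as 376 days does not look odd when the Week 52 diary window in SAP Table 3 extends to Day 385. A programmer who silently corrected the order would be departing from the written SAP, and SAP 1 asks that deviations be justified and reported.

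The objection succeeds on scope. A reader might infer any of three stronger points, and the documents support none of them.

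- **That every interruption inflates exposure.** The + 1 means that a one-day interruption is deducted correctly and a two-day interruption has no effect (stop date inclusive).
- **That the long-term safety results are compromised.** Adverse event incidence in SAP 7.3 is counts and percentages of subjects, with no person-time denominator. The treatment-emergent window in SAP Table 2 uses first and last dose dates, or the end-of-study visit if earlier. No inferential testing of safety data is planned.
- **That the per-protocol sets will be wrong.** The 70% figure is only an example in SAP 3.2, which does not say that it is calculated by SAP 7.2. The exclusions are set in separate deviation specifications and finalised before lock, and the per-protocol analyses are supportive. It would take 36 or 66 days off drug to move an otherwise fully compliant man below 70%.

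**Conclusion.** The formula is wrong as written, and the SAP contradicts itself on the point. With an inclusive stop date, interruptions of three or more days add n − 2 days to exposure and expected doses, an overstatement of 2n − 2 days. The error is 26 days for a 14-day interruption and 54 days for a 28-day one, whatever the course length.

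The outputs affected are the exposure summary and listing, and the compliance summary with its below-80% category. Any effect on per-protocol membership is illustrative only. Adverse event counts and percentages are unaffected.

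The number of men affected cannot be estimated from the documents. The figures rest on one interruption per man, all other doses taken, and a stop date equal to the last day off drug; the last of these changes the result by one day.

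**What to change.** Replace the line in SAP 7.1 with: Interruption in days = date interruption stopped − date interruption started + 1, in agreement with SAP 4.3.3. State in the same place that the stop date is the last day off drug; if it is recorded as the day dosing resumes, omit the + 1. Apply the definition to both adverse event interruptions and resupply gaps, because a gap found by comparing dispensation dates may naturally end on the day drug is dispensed again.

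A useful programming check is that no subject's exposure may exceed last dose date minus first dose date plus 1.

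The cost is one line of SAP text and one sentence of definition before database lock. No data collection, sample size or other analysis changes.
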